5.4. Screen Failures

Participant Identification, Enrollment, and Screening Logs

The investigator agrees to complete a participant identification and enrollment log to permit easy identification of each participant during and after the study. This document will be reviewed by the sponsor study site contact for completeness.

The participant identification and enrollment log will be treated as confidential and will be filed by the investigator in the study file. To ensure participant confidentiality, no copy will be made. All reports and communications relating to the study will identify participants by participant identification and age at initial informed consent. In cases where the participant is not randomized into the study, the date seen and age at initial informed consent will be used.

Individuals who do not meet the criteria for participation in this study (screen failure) may be rescreened. Rescreened participants will be assigned a new participant number, undergo the informed consent process, and then start a new screening period.

5.5. Criteria for Temporarily Delaying Administration of Study Intervention

Guidelines for study intervention administration affected by the COVID-19 pandemic are found in Section [10.9](#), Appendix 9: Study Conduct During A Natural Disaster.

6. STUDY INTERVENTION AND CONCOMITANT THERAPY

6.1. Study Intervention Administered

Study intervention administration must be captured in the source documents and the electronic case report form (eCRF).

Bermekimab will be manufactured and provided under the responsibility of the sponsor. Refer to the [IB](#) for a list of excipients.

For details on rescue medications, refer to Section [6.8.4](#), Rescue Medication. For a definition of study intervention overdose, refer to Section [6.7](#), Treatment of Overdose.

Approximately 10 participants are planned to receive weekly 800 mg of IV bermekimab or placebo in Part A. Approximately 30 participants are planned to receive weekly 1200 mg of IV bermekimab or placebo in Part B. After the initial 10 participants (8A:2P) have completed 6 weeks of dosing in Part B, safety, PK, PD, and efficacy will be analyzed to determine an appropriate dose to be used in Part C. Approximately 20 participants are planned to receive the determined dose of bermekimab and placebo. The maximum dose to be considered for Part C will be 2400 mg IV weekly ([Table 2](#)).

Table 2: Description of Interventions

Part Name	Part A	Part B	Part C	N/A
Intervention Name	bermekimab	bermekimab	bermekimab	Placebo
Dose Formulation	sterile liquid formulation of 350 mg (175 mg/mL) of bermekimab in a prefilled syringe (PFS) with an injectable volume of 2.0 mL.	sterile liquid formulation of 350 mg (175 mg/mL) of bermekimab in a PFS with an injectable volume of 2.0 mL.	sterile liquid formulation of 350 mg (175 mg/mL) of bermekimab in PFS with an injectable volume of 2.0 mL.	Saline vials
Unit Dose Strength(s)	175 mg/mL	175 mg/mL	175 mg/mL	N/A
Dosage Level(s)	800 mg intravenous (IV) infusion weekly from Week 0 through Week 15	1200 mg IV infusion weekly from Week 0 through Week 15	TBD mg IV infusion weekly from Week 0 through Week 15	IV infusion weekly from Week 0 through Week 15
Route of Administration	IV infusion	IV Infusion	IV Infusion	IV Infusion
Use	Experimental	Experimental	Experimental	Placebo comparator
Investigational Medicinal Product	Yes	Yes	Yes	No
Non-Investigational Medicinal Product /Auxiliary Medicinal Product	No	No	No	No
Sourcing	Provided centrally by the sponsor			
Packaging and Labeling	The investigational supplies will be uniquely packaged to assure that they are appropriately managed throughout the supply chain process. Study intervention labels will contain information to meet the applicable regulatory requirements	The investigational supplies will be uniquely packaged to assure that they are appropriately managed throughout the supply chain process. Study intervention labels will contain information to meet the applicable regulatory requirements	The investigational supplies will be uniquely packaged to assure that they are appropriately managed throughout the supply chain process. Study intervention labels will contain information to meet the applicable regulatory requirements	The investigational supplies will be uniquely packaged to assure that they are appropriately managed throughout the supply chain process. Study intervention labels will contain information to meet the applicable regulatory requirements
Delivery instructions	See Investigational Product Preparation Instructions (IPPI)	See IPPI	See IPPI	See IPPI
Current/Former Name or Alias	JNJ-77474462	JNJ-77474462	JNJ-77474462	N/A

6.2. Preparation/Handling/Storage/Accountability

Preparation/Handling/Storage

All study intervention must be stored at controlled temperatures ranging from 36°F to 46°F (2°C to 8°C) and must be protected from light. Placebo must be stored at controlled temperatures, as indicated on the product-specific labeling.

Refer to the IPPI for additional guidance on study intervention preparation, handling, and storage.

Accountability

The investigator is responsible for ensuring that all study intervention received at the site is inventoried and accounted for throughout the study.

The study intervention administered to the participant must be documented on the intervention accountability form. All study intervention will be stored and disposed of according to the sponsor's instructions. Study-site personnel must not combine contents of the study intervention containers.

Study intervention must be handled in strict accordance with the protocol and the container label, and must be stored at the study site in a limited-access area or in a locked cabinet under appropriate environmental conditions. Unused study intervention must be available for verification by the sponsor's study site monitor during on-site monitoring visits. The return to the sponsor of unused study intervention, or used returned study intervention for destruction, will be documented on the intervention return form. When the study site is an authorized destruction unit and study intervention supplies are destroyed on-site, this must also be documented on the intervention return form.

Potentially hazardous materials such as used ampules, needles, syringes and vials containing hazardous liquids, should be disposed of immediately in a safe manner and therefore will not be retained for intervention accountability purposes.

Study intervention should be dispensed under the supervision of the investigator or a qualified member of the study site personnel, or by a hospital/clinic pharmacist. Study intervention may not be relabeled or reassigned for use by other participants. The investigator agrees neither to dispense the study intervention from, nor store it at, any site other than the study sites agreed upon with the sponsor.

6.3. Measures to Minimize Bias: Randomization and Blinding

Intervention Allocation

Procedures for Randomization

Central randomization will be implemented in this study. Participants in Part A, Part B, and Part C will be randomly assigned to either the bermekimab or placebo intervention groups (4:1 ratio) based on a computer-generated randomization schedule prepared before the study by or under the supervision of the sponsor. The randomization will be balanced by using randomly permuted blocks. The interactive web response system (IWRS) will assign a unique intervention code, which

will dictate the intervention assignment and matching study intervention kit for the participant. The requestor must use his or her own user identification and personal identification number when contacting the IWRS, and will then give the relevant participant details to uniquely identify the participant.

Blinding

Active study intervention and placebo will be prepared by an unblinded pharmacist or an unblinded qualified member of the investigational staff while the remainder of site personnel will remain blinded. The volume of the placebo will match the volume of the active intervention in each cohort. Prepared doses may be covered to mask potential visual differences between the active study intervention and placebo. The participants and other site staff members, including the investigator, will be blinded to study intervention allocation through study completion to reduce bias in the assessment of safety and tolerability data. Administration of study intervention to the participants will be performed by a blinded, qualified healthcare provider. Independent drug monitors will be used to monitor drug accountability and all unblinded study data.

The investigator will not be provided with randomization codes. The codes will be maintained within the IWRS, which has the functionality to allow the investigator to break the blind for an individual participant.

Data that may potentially unblind the intervention assignment (ie, study intervention serum concentrations, anti-JNJ-77474462 antibodies, study intervention preparation/accountability data, intervention allocation) will be handled with special care to ensure that the integrity of the blind is maintained and the potential for bias is minimized. This can include making special provisions, such as segregating the data in question from view by the investigators, clinical team, or others as appropriate until the time of DBL and unblinding.

Under normal circumstances, the blind should not be broken until all participants have completed the study and the database is finalized. Otherwise, the blind should be broken only if specific emergency intervention/course of action would be dictated by knowing the intervention status of the participant. In such cases, the investigator may in an emergency determine the identity of the intervention by contacting the IWRS. While the responsibility to break the intervention code in emergency situations resides solely with the investigator, it is recommended that the investigator contact the sponsor or its designee if possible to discuss the particular situation, before breaking the blind. Telephone contact with the sponsor or its designee will be available 24 hours per day, 7 days per week. In the event the blind is broken, the sponsor must be informed as soon as possible. The date and reason for the unblinding must be documented in the appropriate section of the eCRF and in the source document. The documentation received from the IWRS indicating the code break must be retained with the participant's source documents in a secure manner.

For the purpose of the interim analysis of safety data and preliminary PK, efficacy, and PD analysis, designated sponsor personnel will be unblinded to the relevant data as is required (Section 8.4, Pharmacokinetics and Immunogenicity). The randomization code will be disclosed to those authorized and only for those participants included in the interim analysis. All site personnel and participants will remain blinded to the treatment assignments until the last participant completes the Week 20 evaluations and the final database is locked.

Participants who have had their intervention assignment unblinded should continue to return for scheduled evaluations and are not eligible to receive further study intervention.

Additionally, a given participant's treatment assignment may be unblinded to the sponsor, the Independent Ethics Committee/Institutional Review Board (IEC/IRB), and site personnel to fulfill regulatory reporting requirements for suspected unexpected serious adverse reactions (SUSARs).

A separate code break procedure will be available for use by the sponsor's Global Medical Safety group to allow for unblinding of individual participants to comply with specific requests from regulatory or health authorities.

6.4. Study Intervention Compliance

Study intervention will be administered by IV infusion by blinded qualified study-site personnel and the details of each administration will be recorded in the eCRF (including date and time of study intervention administration).

The investigator or designated study-site personnel will maintain a log of all study interventions dispensed and returned. Intervention supplies for each participant will be inventoried and accounted for throughout the study. At all times, study intervention under preparation/administration must be supervised to ensure proper handling and to avoid potential dosing errors or tampering.

Any accidental administration of study intervention to a non-study participant must be reported immediately to the sponsor's medical monitor.

Additional details are provided in the instructions provided by the sponsor (IPPI).

6.5. Dose Modification

No treatment or dose adjustment will be permitted throughout the study.

6.6. Continued Access to Study Intervention After the End of the Study

Participants will be instructed that study intervention will not be made available to them after they have completed/discontinued study intervention and that they should return to their primary physician to determine standard of care.

6.7. Treatment of Overdose

For this study, any dose of bermekimab greater than the highest dose at a single dosing visit within a 24-hour time period will be considered an overdose. The sponsor does not recommend specific treatment for an overdose.

In the event of an overdose, the investigator or treating physician should:

- Contact the Medical Monitor immediately.
- Evaluate the participant to determine, in consultation with the Medical Monitor, whether study intervention should be interrupted or whether the dose should be reduced.
- Closely monitor the participant for AE/SAE and laboratory abnormalities

- Document the quantity of the excess dose as well as the duration of the overdosing in the eCRF.

6.8. Concomitant Therapy

Pre-study therapies administered up to 30 days before the screening visit should be continued. Modification of an effective preexisting therapy should not be made for the explicit purpose of entering a participant into the study.

Every effort should be made to keep participants on stable concomitant medications. If a medication is temporarily discontinued because of abnormal laboratory values, side effects, concurrent illness, or the performance of a procedure, the change and reason for it should be clearly documented in the participant's medical records.

All therapies (prescription or over-the-counter medications, including vaccines, vitamins, herbal supplements; non-pharmacologic therapies such as electrical stimulation, acupuncture, special diets, exercise regimens, or other specific categories of interest) different from the study intervention must be recorded in the eCRF. If a medication is temporarily discontinued because of abnormal laboratory values, side effects, concurrent illness, or the performance of a procedure, the change and reason for it should be clearly documented in the participant's medical records. Modification of an effective pre-existing therapy should not be made for the explicit purpose of entering a participant into the study.

The sponsor must be notified in advance (or as soon as possible thereafter) of any instances in which prohibited therapies are administered. Any questions regarding treatment with concomitant medication during the study, should be directed to the medical monitor.

6.8.1. Atopic Dermatitis Management

Investigators should counsel participants on expected management of their condition prior to randomization into the study. Participants should practice sensitive skin care measures as part of management of AD. These measures include taking infrequent (at most once daily) and brief showers or baths, using warm water (not hot) as tolerated. Moisturizer is best applied immediately after showering or bathing. Participants should use fragrance-free cleansers and avoid antibacterial or deodorant soaps, which may be more irritating to the skin. Participants should launder clothes with fragrance-free detergent and avoid fabric softeners. Participants should try to avoid fabrics that may be more irritating to the skin, such as wool or synthetic fabrics.

6.8.2. Required Treatment

All participants are required to apply moisturizers at least once daily for at least 7 days before randomization and continue the treatment throughout the study (including the safety follow-up period). All types of non-prescription moisturizers are permitted, excluding any moisturizer that contains a corticosteroid.

6.8.3. Prohibited Therapies/Medications

The following therapies will not be allowed during the course of the study.

- Topical corticosteroids, except for rescue therapy (see Section 6.8.4, Rescue Medication)
- Topical calcineurin inhibitors (eg, tacrolimus and pimecrolimus)

- Topical phosphodiesterase inhibitors 4 (eg, crisaborole)
- Leukotriene inhibitors
- Allergen immunotherapy
- Phototherapy (including psoralen and UV-A, UV-B, tanning beds, and excimer laser)
- Bleach baths
- Systemic corticosteroids (oral)
 - A single course of oral systemic corticosteroids per standard of care for conditions other than AD, for a maximum of 10 days, will be allowed. The use of intramuscular (IM) and IV corticosteroid formulations is prohibited, and will lead to participant discontinuation of study intervention.
 - Other route of administration of corticosteroids including those inhaled, otic, ocular, nasal, or other routes of mucosal delivery of corticosteroids are allowed.
- Any systemic therapy, investigational or commercial (approved or off label use), used for the treatment of AD or symptoms of AD (eg, dupilumab)
- Topical and systemic janus kinase inhibitors
- Systemic immunosuppressant, cytotoxic, and immunomodulatory agents, including, but not limited to, methotrexate, azathioprine, cyclosporine, mycophenolate mofetil, and immunomodulatory biologic therapies (eg, guselkumab, risankizumab, secukinumab, rituximab, alemtuzumab, abatacept, or visilizumab)
- Any prescription topical treatment for AD, including prescription moisturizer, unless the prescribed moisturizer can be obtained OTC and it doesn't require a prescription.
- Interlukin-1 α inhibiting agents (eg, anakinra, rilonacept, canakinumab)
- Live vaccines, including BCG vaccine.

The sponsor must be notified in advance (or as soon as possible thereafter) of any instances in which prohibited therapies are administered.

6.8.4. Rescue Medication

In the event that a participant experiences any unacceptable or worsening symptoms of AD, investigators should first attempt to control symptoms in participants with moisturizers by increasing the frequency of use to at least twice a day and by reemphasizing other permitted skin care measures. However, if these measures are insufficient to control symptoms, investigators will have the option to treat with protocol-allowed rescue therapy. The rationale for rescue must be documented in source.

Hydrocortisone 2.5% ointment may be given to the participant for rescue treatment of any problem areas on the body unless otherwise contraindicated in that participant. In the event that hydrocortisone 2.5% ointment is not available for use in the locale of a study site, an alternate, equivalent potency topical corticosteroid may be supplied.

Participants should use rescue therapy only for as long as necessary to control problem areas, or for a maximum of 2 consecutive weeks. Participants using rescue by topical therapy will continue

to take investigational product and use of rescue therapy will be documented in the eCRF. No more than 2 rounds of rescue therapy may be used by a participant, and these rounds must be separated by at least 1 week.

If topical rescue therapy as stipulated above fails to control AD symptoms sufficiently, the investigator should consider discontinuing the participant from the study.

For guidelines on management of IRR, refer to Section 2.3.1, Benefit-Risk Assessment for Study Participation.

6.8.5. Drugs Metabolized by Cytochrome P450

In vitro studies have shown that IL-1 could impact cytochrome (CYP) enzyme expression and activities (Renton 2005; Abdel-Razzak 1993). As such, suppression of IL-1 α by bermekimab, a cytokine modulator, may potentially alter the hepatic metabolism and clearance of drugs that are substrates for CYP enzymes (Food and Drug Administration [FDA] Guidance 2020). Therefore, upon initiation or discontinuation of bermekimab in participants being treated with CYP substrates with a narrow therapeutic index, monitoring of the effect (eg, warfarin) or drug concentration (eg, theophylline) is recommended and the individual dose of the drug may be adjusted as needed.

6.8.6. Vaccinations (including COVID-19)

Concomitant therapies (including any authorized for emergency use or fully approved, eg, COVID-19 or influenza vaccination) must be recorded throughout the study beginning with start of the first dose of study intervention to 4 weeks after the last dose of study intervention. Concomitant therapies should also be recorded beyond that point only in conjunction with SAEs that meet the criteria outlined in Serious Adverse Events in Section 8.3.1, Time Period and Frequency for Collecting Adverse Event and Serious Adverse Event Information.

When considering use of locally-approved (including emergency use-authorized) COVID-19 vaccines in study patients, follow applicable local vaccine labelling, guidelines, and standards of care for patients receiving immune-targeted therapy. For study participants receiving a locally-approved (including emergency use-authorized) COVID-19 vaccine, in order to help identify acute reactions potentially related to COVID-19 vaccine, it is recommended where possible that vaccine and study drug be administered on different days, separated by as large an interval as is practical within the protocol.

7. DISCONTINUATION OF STUDY INTERVENTION AND PARTICIPANT DISCONTINUATION/WITHDRAWAL

7.1. Discontinuation of Study Intervention

A participant's study intervention must be discontinued if:

- The participant withdraws consent to receive study intervention.
- The investigator believes that for safety reasons or tolerability reasons (eg, AE) it is in the best interest of the participant to discontinue study intervention
- Participants who experience a Grade ≥ 3 IRR should be discontinued from the study
- The participant has a serious adverse reaction that is related to an infusion of the study drug administration including a hypersensitivity reaction resulting in bronchospasm, wheezing and/or dyspnea that requires ventilatory support OR that results in symptomatic hypotension with a decrease in systolic blood pressure of 30% from a participant's baseline value or systolic blood pressure <90 mm Hg ([Sampson 2006](#)). In general, discontinuation of study intervention administration must be considered for participants who develop a nonserious but severe infusion-related reaction.
- The participant has a reaction resulting in myalgia and/or arthralgia with fever and/or rash (suggestive of serum sickness and not representative of signs and symptoms of other recognized clinical syndromes) occurring 1 to 14 days after an infusion of study intervention. These may be accompanied by other events including pruritus, facial, hand, or lip edema, dysphagia, urticaria, sore throat, and/or headache.
- The participant becomes pregnant or plans a pregnancy during the study period. Refer to [Section 10.5](#), Appendix 5: Contraceptive and Barrier Guidance.
- The initiation of protocol-prohibited medications, treatments, or interventions (outlined in [Section 6.8](#), Concomitant Therapy) that have an impact on AD efficacy evaluations.
- The participant has a malignancy including squamous cell skin cancer. Consideration may be given to allow participants, who develop ≤ 2 basal cell skin cancers and who are adequately treated with no evidence of residual disease, to continue to receive study intervention.
- A systemic opportunistic infection.
- A recurrent or chronic serious infection.
- The participant is deemed ineligible according to the following TB screening criteria:
 - A diagnosis of active TB is made.
 - A participant has symptoms suggestive of active TB based on follow-up assessment questions and/or physical examination or has had recent close contact with a person with active TB and cannot or will not undergo additional evaluation.
 - A participant undergoing evaluation has a chest radiograph with evidence of current active TB and/or a positive QuantiFERON-TB test result and/or 2 indeterminate QuantiFERON-TB test results on repeat testing (refer to [Section 8.2.9](#), Tuberculosis Evaluations) (and/or a positive tuberculin skin test result in countries in which the QuantiFERON-TB test is not approved/registered or the tuberculin skin test is mandated by local health authorities).

- A participant receiving treatment for latent TB discontinues this treatment prematurely or is noncompliant with the therapy.
- The participant is unable to adhere to the study visit schedule or comply with protocol requirements.
- Abnormal liver tests as outlined in Section 10.7, Appendix 7: Liver Safety: Suggested Actions and Follow-Up Assessments.
- Use of prohibited corticosteroids:
 - IM and IV formulations
 - Oral corticosteroids for more than 10 days.
- The participant has his/her treatment assignment unblinded by the investigator.
- Sponsor decision.

If a participant discontinues study intervention for any reason before the end of the double-blind phase, then the end-of-intervention assessments should be obtained and scheduled assessments off study intervention should be continued. Study intervention assigned to the participant who discontinued study intervention may not be assigned to another participant. Additional participants will not be entered.

Participants who decide to discontinue study intervention administration for reasons other than those outlined above must be interviewed by the investigator to determine if a specific reason for discontinuing study intervention can be identified. Participants should be explicitly asked about the possible contribution of AEs to their decision to discontinue study intervention; investigators should confirm that any AE information elicited has been documented. If a participant elects to discontinue study intervention due to an AE, the event should be recorded as the reason for study intervention discontinuation, even if the investigator's assessment is that the AE would not require study intervention discontinuation. The reason for study intervention discontinuation must be documented in the eCRF and in source documents. Study intervention assigned to a participant who discontinues may not be assigned to another participant.

A participant will not be automatically withdrawn from the study if he or she must discontinue treatment before the end of the treatment regimen. Participants who discontinue study intervention but do not terminate study participation are strongly encouraged to return for all protocol-specified procedures and evaluations for approximately 5 weeks following the last dose of study intervention. The procedures and evaluations listed for the early termination visit should also be performed approximately 5 weeks after the last dose of study intervention.

All procedures and evaluations must be conducted prior to a participant's withdrawal of consent.

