Participants who experience close contact with an individual with active TB during the conduct of the study must have a repeat chest radiograph, a repeat QuantiFERON-TB (or T-SPOT for sites in Japan) test, a repeat tuberculin skin test in countries in which the QuantiFERON-TB test is not approved/registered or the tuberculin skin test is mandated by local health authorities, and, if possible, referral to a physician specializing in TB to determine the participant’s risk of developing active TB and whether treatment is warranted. Study intervention administration should be interrupted during the investigation. A positive QuantiFERON-TB (or T-SPOT for sites in Japan) test or tuberculin skin test result should be considered detection of latent TB. Participants with a newly identified positive QuantiFERON-TB (or T-SPOT for sites in Japan or tuberculin skin) test result must undergo an evaluation to rule out active TB and initiate appropriate treatment for latent TB. Appropriate treatment for latent TB is defined according to local country guidelines for immunocompromised participants. If no local country guidelines for immunocompromised participants exist, US guidelines should be followed, or the participant will be excluded from the study. If the QuantiFERON-TB test result is indeterminate, the test should be repeated. For sites in Japan, a participant whose first T-SPOT test result is borderline should have the test repeated. Participants should be encouraged to return for all subsequent scheduled study visits according to the protocol. Participants who discontinue treatment for latent TB prematurely or who are noncompliant with therapy must immediately discontinue further administration of study

intervention and be encouraged to return for all subsequent scheduled study visits according to the SoA (Section 1.3).

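### After a positive TB test on study, Section 7.1 requires study intervention to be discontinued, while Section 8.2.9.2 implies that dosing may continue under latent TB treatment

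*Protocol*

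**What the plan says.** Protocol Section 7.1 opens its list with a mandatory instruction: "A participant's study intervention must be discontinued if" any of the listed events occurs. The TB items sit under the parent line "The participant is deemed ineligible according to the following TB screening criteria". One of them concerns a participant undergoing evaluation whose chest radiograph shows current active TB "and/or a positive QuantiFERON-TB test result and/or 2 indeterminate QuantiFERON-TB test results on repeat testing". It extends to a positive tuberculin skin test in countries where QuantiFERON is not approved or the skin test is mandated, and it refers the reader to Section 8.2.9. The next item is a separate trigger: "A participant receiving treatment for latent TB discontinues this treatment prematurely or is noncompliant with the therapy".

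Protocol Section 8.2.9.2 covers evaluation during the study. After close contact with someone who has active TB, the participant has a repeat radiograph and a repeat QuantiFERON test, plus a skin test where applicable. On dosing it says: "Study intervention administration should be interrupted during the investigation". A positive QuantiFERON "test or tuberculin skin test result should be considered detection of latent TB", and a participant with a newly positive result "must undergo an evaluation to rule out active TB and initiate appropriate treatment for latent TB". The section then says that those who stop latent TB treatment early, or do not comply with it, must immediately stop receiving study intervention.

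**The concern.** Both sections apply to the same participant: one who is tested on study because of TB exposure and comes back positive. Section 7.1 read alone ends dosing on the test result. Section 8.2.9.2 read alone pauses dosing for the investigation, starts latent TB treatment, and makes discontinuation depend on how the participant manages that treatment. Section 7.1 sends the reader to 8.2.9, so a careful site will meet both instructions.

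TB is a named risk in the protocol's benefit-risk table, and this is a stopping rule for it. At stake is whether participants with the same result are handled in the same way, and whether a site acting in good faith on one section is then recorded as having breached the other.

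**Working it through.** The point has no numerical input, so the check is a comparison of the texts.

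1. **Do the two sections cover the same event?** Yes, for a positive test. The 7.1 item applies to a participant undergoing evaluation, and 8.2.9.2 describes such an evaluation after close contact. The and/or links in 7.1 mean that the positive test does not need an abnormal radiograph with it. The item has no exception for latent TB once active TB is ruled out.

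2. **Are discontinuation and interruption different actions in this protocol?** Yes. The infection row of Table 1 in Section 2.3.1 uses discontinuation for opportunistic infection including TB. It uses interruption for serious infection, with continuing or stopping to be decided afterwards.

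3. **Does 8.2.9.2 allow dosing to go on after a positive test?** It does not say so outright. It attaches the interruption to the contact investigation, and attaches evaluation and latent TB treatment to the positive result. Its closing rule orders immediate discontinuation if latent TB treatment is stopped early or not followed. That order has content only for someone on latent TB treatment who can still receive study intervention. Because it follows directly on the instructions for newly positive participants, the natural reading is that those who comply may continue.

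4. **Does the entry rule settle it?** No. Section 7.1 describes its TB triggers as ineligibility under screening criteria. Inclusion criterion 19 nevertheless admits a participant with a newly positive QuantiFERON if active TB has been ruled out and latent TB treatment has been started. A positive test alone is therefore not disqualifying at entry, and the 7.1 label does not resolve the difference.

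5. **Is there a further loose end?** Where no local guideline for immunocompromised participants exists, 8.2.9.2 says that US guidelines apply or the participant is excluded from the study. That adds another possible outcome without saying when it applies.

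6. **Where would the difference show in the outputs?** SAP Appendix 4 lists major deviations, including a category for participants who met withdrawal criteria but were not withdrawn. A participant kept on study intervention under 8.2.9.2 could be placed there by someone applying 7.1. SAP Section 5.2 also lists participants who discontinued study intervention, so membership of that listing depends on which section the site followed.

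7. **Does it change the primary endpoint?** Not by classification. A discontinuation for this reason would be intercurrent event 4 in protocol Section 9.4.2, which is handled by treatment policy. If the Week 16 EASI is obtained, the participant is scored from the observed value, as is a participant with no intercurrent event.

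**The case against.** The strongest reply is that the sections can be read in sequence: interrupt dosing during the investigation (8.2.9.2), discontinue if the test is positive (7.1), then treat latent TB off study drug as medical care (8.2.9.2). Section 7.1 is the stopping list. Section 8.2.9.2 never says that dosing resumes and does not present its one trigger as complete. Its encouragement to return for later visits fits off-drug follow-up. The rule on abandoning latent TB treatment would still reach participants who entered the study on such treatment, as criterion 19 allows.

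Part of this stands. Continued dosing under 8.2.9.2 is an inference, and the interruption is tied to the contact, not to the test result. But the sequential reading leaves the rule on treatment adherence with no effect for newly positive participants, the group that the preceding sentences describe. A site should not have to reconstruct a stopping rule in this way when two readings are available.

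A reader might also infer a contradiction for two indeterminate results, since 7.1 names them in the same item. The documents do not support that. For on-study testing, 8.2.9.2 says only to repeat an indeterminate test and gives no action after a second one, so 7.1 is the only on-study rule. The text that permits a participant to go forward after a second indeterminate result is in Section 8.2.9.1 and concerns enrolment.

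**Conclusion.** The inconsistency holds for a positive on-study TB test: 7.1 requires discontinuation, and 8.2.9.2 implies that a participant who complies with latent TB treatment may continue. This rests on reading the adherence rule in 8.2.9.2 as applying to the newly positive participants just described.

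The size is limited and cannot be put as a number. The documents give no frequency. The Schedule of Activities places QuantiFERON at screening only, so an on-study result would come from unscheduled testing, such as after a contact. The effect is on safety handling and on the consistency of deviation and discontinuation listings.

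Two stronger readings should be set aside. A reader might take 7.1 to require permanent discontinuation. It does not use that word; what it states is a mandatory discontinuation. A reader might also express the effect as one participant's share of a treatment group, for example 1/12 = 8.3 percentage points in the planned pooled placebo group. That is only the weight of one participant. The wording conflict does not itself change a response, because intercurrent event 4 uses observed data. The SAP also states that the study ended early, with listings and no formal analyses, so no planned analysis depends on this point.

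**What to change.** The sponsor should reconcile Sections 7.1 and 8.2.9.2 so that a single stated action on study intervention follows a positive on-study QuantiFERON or, where applicable, tuberculin skin test, with the same wording or a direct cross-reference in both places. The reconciled text should say explicitly what happens to dosing once the investigation is complete, and whom the rule on adherence to latent TB treatment covers. Which action applies is a clinical decision for the sponsor, and none is proposed here.

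The cost is a wording change in a protocol amendment, with no effect on design, sample size or analysis. If no amendment is to be issued because the study has ended early, the low-cost alternative is to note in the deviation and discontinuation listings which section was applied to any participant who tested positive on study.
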